8.4.4 Safety analyses

Evaluations of safety will be performed using the safety analysis set. The incidence of AEs and SAEs will be tabulated using frequency count.

8.4.5 Planned interim analyses

There are no planned interim analyses for this study.

8.4.6 Sub-group analyses

Not Applicable

9 SUPPORTING DOCUMENTATION AND OPERATIONAL CONSIDERATIONS

9.1 Regulatory, Ethical, and Study Oversight Considerations

9.1.1 Informed consent process

By signing the protocol, the investigator assures that informed consent/assent will be obtained from each parent/legal guardian prior to study entry and that the informed consent/assent will be obtained in accordance with current regulations.

The investigator or sub-investigator will give each parent/legal guardian full and adequate verbal and written information regarding the objectives and procedures of the study and the possible risks involved. An informed consent/assent document will be provided to each parent/legal guardian in a language in which the parent/legal guardian is fluent. This information must be provided to the parent/legal guardian prior to undertaking any study related procedure. Adequate time should be provided for the parent/legal guardian to read the informed consent, to understand the risks and benefits of participating in the study, and to ask any questions that the parent/legal guardian may have about the study. The parent/legal guardian should be able to ask additional questions as and when needed during the conduct of the study. Where applicable, the subject will sign an age-appropriate assent form.

Each parent/legal guardian will be given a copy of the signed consent/assent form. The original signed informed consent forms will be retained by the investigator with the study records.

The written subject information must not be changed without prior approval by PTC Therapeutics and the IRB/EC.

9.1.2 Study discontinuation and closure

PTC Therapeutics reserves the right to discontinue the study prior to inclusion of the intended number of subjects. The investigator, after consultation with the PTC Therapeutics medical monitor, reserves the right to discontinue the study at the investigator site for safety reasons at any time.

After a decision to terminate the study, investigators must contact all subjects who are continuing their participation in the study and must do so within a time period set by PTC Therapeutics. As directed by PTC Therapeutics, all study materials must be collected, and all electronic data entry forms completed to the greatest extent possible.

9.1.3 Confidentiality and privacy

Research records will be collected and stored in a manner that protects the confidentiality of subject information. The names and identities of all research subjects will be kept in strict confidence and will not appear on eCRFs, paper CRFs, or other records provided to or

retained by PTC Therapeutics (or its authorized designee). The names and identities of the subjects need not be divulged; however, the records must nevertheless be inspected. This will be accomplished by blanking out the subject's name and replacing the name with the subject's study identification number on any record provided to or retained by PTC Therapeutics. The informed consent form must include appropriate statements explaining these requirements.

By signing this protocol, the investigator affirms to PTC Therapeutics that the investigator will maintain, in confidence, information furnished by PTC Therapeutics and will divulge such information to the IRB/IEC under an appropriate understanding of confidentiality with such board.

9.1.4 Future use of stored specimens and data

As part of the current study, muscle tissue via biopsies will be collected to evaluate the effect of ataluren treatment on the expression of dystrophin protein as measured by ECL and immunohistochemistry. Sample processing will be performed by laboratories under the direction of the sponsor. Processing, analysis, and storage will be performed at a secure laboratory facility to protect the validity of the data and maintain subject privacy.

The samples will be stored for 10-years. Only PTC Therapeutics and its representatives and agents will have access to muscle biopsy/extracts and they will not be shared with secondary researchers.

These same samples will potentially be used to look at biochemical biomarkers that may be altered due to increased dystrophin levels and to generate new hypotheses (eg, identify factors involved in disease progression and identify possible new drug targets). No additional genetic testing will be performed or cell lines created. The results will be communicated to PTC Therapeutics.

The subject/parent/caregiver will provide confirmation to allow any remaining specimens to be used for exploratory research work by PTC Therapeutics within the Informed Consent Form (ICF). The ICF will contain a separate authorization for the use of remaining tissue for exploratory research. Subjects/parents/caregivers will be told that participation in exploratory research is optional and that they can decline participation in this research. Subjects/parents/caregivers may withdraw their consent and request disposal of their stored samples at any time and for any reason during the storage period.

No subject-identifying information (eg, initials, date of birth, government identifying number) will be associated with any of the biologic samples. All samples will be single coded and the sponsor will take steps to ensure that data are protected accordingly, and confidentiality is maintained to the extent possible.

Given the research nature of the analysis, it will not be possible to return individual data to subjects. The results that may be generated are not currently anticipated to have clinical relevance to the patients or their family members. Therefore, these results will not be disclosed to the patients or their physicians.

9.1.5 Clinical monitoring

In accordance with 21 Code of Federal Regulations Part 312.56 and/or relevant ICH (International Council for Harmonisation) guidelines, PTC Therapeutics or a designee will periodically inspect all eCRFs, study documents, research facilities, and clinical laboratory facilities associated with this study at mutually convenient times, before, during, and after completion of the study. As required by applicable regulations (Responsibilities of Sponsors and Investigators), the monitoring visits provide PTC Therapeutics with the opportunity to evaluate the progress of the study; verify the accuracy and completeness of data in the eCRFs; ensure that all protocol requirements, relevant regulations, and investigator's obligations are being fulfilled; and resolve any inconsistencies in the study records. This includes inspection of all documents and records required to be maintained by the Investigator, including but not limited to medical records (office, clinic, or hospital) for the subjects in this study. The names and identities of all research subjects will be kept in strict confidence and will not appear on eCRFs or other records provided to or retained by PTC Therapeutics. The investigator/institution guarantees direct access to source documents by PTC Therapeutics and appropriate regulatory authorities.

It is important that the investigator and relevant institutional personnel are available during the monitoring visits and possible audits or inspections and that sufficient time is devoted to the process.

9.1.6 Quality assurance and quality control

To ensure compliance with GCP (Good Clinical Practice) and all applicable regulatory requirements, PTC, PTC's representatives, a regulatory authority or and Institutional Review board may conduct a quality assurance audit. Reasons for quality assurance audit may include but are not limited to: random selection, geographic proximity, suspected GCP violation, high enrolling site, recurring protocol deviations, etc. The purpose of a Sponsor audit or inspection is to systematically and independently examine all study-related activities and documents to determine whether these activities were conducted, and data were recorded, analyzed, and accurately reported according to the protocol, Good Clinical Practice guidelines of the International Council for Harmonisation, and any applicable regulatory requirements. The Investigator should contact the Sponsor immediately if contacted by a regulatory agency about an inspection.

9.1.7 Data handling and record keeping

To enable evaluations and/or audits from regulatory authorities or PTC Therapeutics, the investigator agrees to keep accurate and complete records, including the identity of all participating subjects (sufficient information to link eCRFs and clinic records/source documents), all original signed informed consent forms, electronic copies (ie, CD-ROM, USB, etc.) or paper copies of the data that have been captured in the EDC for each subject (eCRFs), and detailed records of study drug disposition. All records and documents pertaining to the study will be maintained by the investigator until notification is received from PTC Therapeutics that the records no longer need to be retained.

The investigator must obtain written permission from PTC Therapeutics before disposing of any records. The investigator will promptly notify PTC Therapeutics in the event of accidental loss or destruction of any study records. If the investigator relocates, retires, or for any reason withdraws from the study, the study records may be transferred to an acceptable designee, such as another investigator, another institution, or to PTC Therapeutics as applicable.

9.1.8 Protocol deviations

A protocol deviation is defined as any intentional or unintentional change to, or noncompliance with, the approved protocol procedures or requirements. Deviations may result from the action or inaction of the subject, investigator, or site staff. Examples of deviations include, but are not limited to:

- Failure to adhere to study exclusion and inclusion criteria
- Use of medications that are specifically prohibited in the protocol
- Missed or out-of-window visits
- Failure to adhere to test requirements, including vital signs, laboratory tests, physical examinations, PK blood draws, medical history, etc. – either tests not done, incorrect tests done, or not done within the time frame specified in the protocol
- Procedural deviations, failure to update the ICF when new risks become known, or failure to obtain IRB approvals for the protocol and ICF revisions

Significant deviations are any deviations that impact subject eligibility (ie, protocol inclusion/exclusion violations), subject safety or a subject's ability to continue in the clinical trial.

At the outset of the study, a process for defining and handling protocol deviations will be established with the CRO. This will include determining which deviations will be designated significant; thus, requiring immediate notification to the PTC Therapeutics medical monitor and the sponsor.

Prospective deviations (eg, protocol waivers) are prohibited per PTC policy.

The investigator is responsible for seeing that any known protocol deviations are recorded handled as agreed.

9.1.9 Publication and data sharing policy

The information developed during the conduct of this clinical study is considered confidential by PTC Therapeutics. This information may be disclosed as deemed necessary by PTC Therapeutics.

PTC Therapeutics intends that the data from this study will be presented and published. The PTC Therapeutics staff under the direction of the PTC Therapeutics Chief Medical Officer or designee in collaboration with the investigator will be responsible for writing presentations and manuscripts for publication. Investigators will not be allowed to publish or present the data from this study without prior agreement with PTC Therapeutics.

The investigator is obliged to provide the sponsor with complete test results and all data derived by the investigator from the study. During the study, only the sponsor may make study information available to other study Investigators or to regulatory agencies, except as required by law or regulation. Except as otherwise allowable in the clinical study site agreement, any public disclosure (including publicly accessible websites) related to the protocol or study results, other than study recruitment materials and/or advertisements, is the sole responsibility of the Sponsor.

The sponsor may publish any data and information from the study (including data and information generated by the investigator) without the consent of the Investigator. Manuscript authorship for any peer-reviewed publication will appropriately reflect contributions to the production and review of the document. All publications and presentations must be prepared in accordance with this section and the Clinical Study Site Agreement. In the event of any discrepancy between the protocol and the Clinical Study Site Agreement, the Clinical Study Site Agreement will prevail.

Data from all sites participating in the study will be pooled and analyzed by the sponsor or the sponsor's designee. The first publication of the study results shall be made in conjunction with the results from other study sites as a multicenter publication. If a multicenter publication is not forthcoming within 24 months of completion of the study at all sites, the investigator may publish or present the results generated at his or her site.

The investigator will provide the sponsor with a copy of any proposed publication or presentation for review and comment at least 60 days prior to such presentation or submission for publication. The sponsor shall inform the investigator in writing of any changes or deletions in such presentation or publication required to protect the sponsor's confidential and proprietary technical information and to address inaccurate data or inappropriate interpretations in the context of any pooled multicenter results. At the expiration of such 60-day period, the investigator may proceed with the presentation or submission for publication unless the sponsor has notified the institution or the investigator in writing that such proposed publication or presentation discloses the sponsor's confidential and proprietary technical information. Further, upon the request of the sponsor, the investigator will delay the publication or presentation for an additional 90 days to permit the sponsor to take necessary actions to protect its intellectual property interests.

9.2 Additional Considerations

Not applicable

9.3 Protocol Amendment History

Original Protocol Issued: 12 Nov 2018

Amendment 1 (20 Mar 2019)

The overall reason for the amendment: The overall reason for the amendment was to ensure that sufficient muscle tissue for analysis was obtained from the biopsy procedure.

Item No.	Protocol Section	Amendment/Update	Reason/Rationale
1	Synopsis	Changed from, "██████ muscle biopsy samples will be collected from the ██████ and ██████." to "A total of no more than approximately 450 mg of muscle tissue (up to ██████ cores per muscle) will be obtained from the ██████ and ██████."	To ensure sufficient muscle tissue for analysis
2	Synopsis	Inclusion criteria #4 changed from, "Currently being treated with ataluren 10, 10, 20 mg/kg for ≥9 months, with no gap in treatment of >1 month, in an ongoing PTC-sponsored nmDMD clinical trial prior to study entry." to "Currently being treated with ataluren 10, 10, 20 mg/kg for ≥9 months, with no gap in treatment of >1 month prior to study entry."	To allow IND subjects to be included
3	List of Abbreviations	Changed from, "International Conferences on Harmonisation" to "International Council for Harmonisation"	Correction
4	Section 3.1	Changed from, "Approximately, 6 ambulatory nmDMD male subjects who have been receiving ataluren, dosed daily 10 mg/kg in the morning, 10 mg/kg at midday, and 20 mg/kg in the evening (10, 10, 20 mg/kg), for ≥9 months from ongoing PTC-sponsored nmDMD clinical trials." to "Approximately, 6 ambulatory nmDMD male subjects who have been receiving ataluren, dosed daily 10 mg/kg in the morning, 10 mg/kg at midday, and 20 mg/kg in the evening (10, 10, 20 mg/kg), for ≥9 months."	To allow IND subjects to be included
5	Section 3.1.1	Changed from, "A total of ██████ cores from each muscle will be obtained." to "A total of no more than approximately 450 mg of muscle tissue (up to ██████ cores per muscle) will be obtained."	To ensure sufficient muscle tissue for analysis
6	Section 3.2	Changed from, "Three muscle biopsy samples will be collected from the ██████ and ██████." to "A total of no more than approximately 450 mg of muscle tissue (up to ██████ cores per muscle) will be obtained from the ██████ and ██████."	To ensure sufficient muscle tissue for analysis
7	Section 4.2	Inclusion criteria #4 changed from, "Currently being treated with ataluren 10, 10, 20 mg/kg for ≥9 months, with no gap in treatment of >1 month, in an ongoing PTC-sponsored nmDMD clinical trial prior to study entry." to "Currently being treated with ataluren 10, 10, 20 mg/kg for ≥9 months, with no gap in treatment of >1 month prior to study entry."	To allow IND subjects to be included

**PTC124-GD-046-DMD
Clinical Protocol**

Item No.	Protocol Section	Amendment/Update	Reason/Rationale
8	Section 5.1	Changed from, "Subjects will be recruited from ongoing PTC sponsored nmDMD clinical trials who currently have been receiving ataluren therapy for ≥9 months." to "Subjects who currently have been receiving ataluren therapy for ≥9 months will be recruited."	To allow IND subjects to be included
9	Section 7.3.1	Changed from, 
 • "All AEs during the study visit and follow-up, including AEs related to the muscle biopsy" to • "All AEs relating to the muscle biopsy" 	Correction
10	Section 7.3.3	Section deleted	Reference Safety Information (RSI) in the ataluren IB does not apply to muscle biopsies
11	Section 8.4.2	Changed from, "The dystrophin level will be summarized by muscle biopsy locations [REDACTED] using descriptive statistics based on ITT analysis set." to "The dystrophin level will be summarized by muscle biopsy locations using descriptive statistics based on ITT analysis set."	To allow biopsy from the [REDACTED] muscle if [REDACTED] muscle is considered by the investigator to be too small for muscle biopsy sampling.
12	Section 9.1.5	Changed from, "International Conferences on Harmonisation" to International Council for Harmonisation"	Correction
13	Section 9.1.6	Changed from, "International Council on Harmonisation" to "International Council for Harmonisation"	Correction
14	Synopsis and Protocol	Document date/version and TOC were updated.	Update

1 INTRODUCTION

Under the current standard of care, nonsense mutation Duchenne muscular dystrophy (nmDMD) remains a disease with devastating consequences and bleak prognosis. The progressive and irreversible effects of nmDMD underscore the importance of early intervention with treatments that have the potential to slow physical deterioration and delay the natural course of this fatal disease. While treatment with corticosteroids target the inflammatory component of the disease, additional treatments are needed to address the loss of dystrophin, the underlying cause of the disease.

The mechanism by which ataluren restores dystrophin has been established in comprehensive preclinical studies and supported in clinical evaluations. Moreover, the clinical benefit of ataluren has been demonstrated in two large randomized controlled trials PTC124-GD-007-DMD (hereafter referred to as Study 007) and PTC124-GD-020-DMD (hereafter referred to as Study 020).

The purpose of this statistical analysis plan (SAP) is to describe the procedures and the statistical methods that will be used in analyzing and reporting results for study PTC124-GD-046-DMD (hereafter referred to as Study 046). This SAP is prepared based on the study protocol V2.0 (dated 08Mar2019).

2 STUDY DESIGN

This is a single-site, non-interventional study designed to generate data on the effect of ataluren for producing dystrophin protein in nmDMD subjects. This study will evaluate dystrophin levels from approximately 6 ambulatory nmDMD male subjects who have been receiving ataluren, dosed daily 10 mg/kg in the morning, 10 mg/kg at midday, and 20 mg/kg in the evening (10, 10, 20 mg/kg), for ≥ 9 months from ongoing PTC-sponsored nmDMD clinical trials.

The study will have a single visit (Visit 1) which will occur at the site of [REDACTED]. At this visit, inclusion/exclusion criteria, demographics and medical history will be assessed. In addition, blood will be drawn for clinical labs and pharmacokinetics (PK) analysis pre-morning ataluren dose. A second blood sample for PK will also be taken 2 hours after morning ataluren dose. The muscle biopsy will also be performed at this visit. Adverse events will be monitored at Visit 1 and by a follow-up phone call approximately 1-week post Visit 1.

Muscle biopsy of the [REDACTED] and [REDACTED] muscles will be performed using an established core muscle biopsy procedure. If the [REDACTED] muscle is considered by the investigator to be too small for a muscle biopsy sample, the [REDACTED] muscle may be used. A total of no more than approximately 450mg of muscle tissue (up to [REDACTED] cores per muscle) from each muscle will be obtained. Vacuum needle muscle biopsy will be performed using local anesthesia or mild sedation, if needed. All biopsies will be preserved/frozen using standard protocol for electrochemiluminescence (ECL) and immunohistochemistry (IHC).

3 STUDY OBJECTIVES AND ENDPOINTS

3.1 Study Objectives

3.1.1 Primary Objective

To assess the levels of dystrophin in ambulatory nmDMD subjects currently being treated with ataluren for ≥ 9 months using a quantitative electrochemiluminescence (ECL) assay.

3.1.2 Secondary Objective

To assess dystrophin levels/intensity and protein localization by immunohistochemistry.

3.1.3 Pharmacokinetic

To evaluate the steady state pharmacokinetics (PK) of ataluren.

3.2 Study Endpoints

3.2.1 Primary Endpoint

Mean dystrophin levels as measured by ECL.

3.2.2 Secondary Endpoint

Levels and localization of dystrophin protein levels as determined by immunohistochemistry.

3.2.3 Pharmacokinetic

PK assessments using sparse sampling and population PK modeling in a separate report. The parameters include CI/F, V/F, AUC₀₋₂₄, C_{max}, and C_{ave}.

3.3 Sample Size

No formal sample size calculation is performed for this study. The sample size was determined empirically based on feasibility and subject availability.

4 STUDY POPULATIONS

4.1 Screened Population

Screened population is defined as all patients who has signed informed consent.

4.2 Enrolled Population

Enrolled population is defined as the subset of screen population who are not screen failures.

4.3 Intent to Treat (ITT) Population

This analysis set will include all enrolled subjects with a valid assessment of dystrophin level, as measured by ECL.

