4 STUDY POPULATION

4.1 Overview

4.2 Inclusion Criteria

1. Evidence of signed and dated informed consent/assent document(s) indicating that the subject (and/or his parent/legal guardian) has been informed of all pertinent aspects of the trial.
2. Male sex.
3. Ambulatory (ie, 10m walk/run in <30seconds) and functional grade on the Brooke Upper Extremity Scale of a 1 or a 2.
4. Currently being treated with ataluren 10, 10, 20 mg/kg for ≥ 9 months, with no gap in treatment of >1 month, prior to study entry.
5. Phenotypic evidence of DMD based on the onset of characteristic clinical symptoms or signs (eg, proximal muscle weakness, waddling gait, and Gowers' maneuver) by 6 years of age and an elevated serum creatine kinase (CK). Medical documentation of phenotypic evidence of DMD needs to be provided upon request by the PTC Therapeutics medical monitor.
6. Willing to undergo muscle biopsy.

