6 SUBJECT DATA

6.1 Subject Disposition and Study Populations

The number of subjects in each analysis population will be summarized using frequency count.

The number of subjects who completed or discontinued from the study and the reasons of discontinuation will be summarized based on the ITT populations.

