6.4 Demographic and Baseline Characteristics

Demographic and baseline characteristics including age at biopsy date, ethnicity group, race, weight, height, and BMI at biopsy date will be summarized based on the ITT populations.

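### Disposition is summarised on a set that requires a valid ECL result, so an enrolled subject who never has one is missing from the completion and reasons table

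*SAP*

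**What the plan says.** SAP 4.3, in the same words as Protocol 8.2.1, defines ITT thus: "This analysis set will include all enrolled subjects with a valid assessment of dystrophin level, as measured by ECL".

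SAP 6.1 does two things. It counts populations: "The number of subjects in each analysis population will be summarized using frequency count". It then reports disposition on the restricted set: "The number of subjects who completed or discontinued from the study and the reasons of discontinuation will be summarized based on the ITT populations". SAP 6.4 uses the same set for demographics and ties the measurements to the biopsy: "weight, height, and BMI at biopsy date will be summarized based on the ITT populations".

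The SAP also has two wider sets. In 4.1: "Screened population is defined as all patients who has signed informed consent". In 4.2: "Enrolled population is defined as the subset of screen population who are not screen failures". Apart from the population count, no summary uses either.

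For safety, SAP 4.4 and Protocol 8.3 ask only for one dose of ataluren. SAP 8.1 counts an adverse event as treatment-emergent (TEAE) when it occurs on or after the biopsy date. SAP 7 places all efficacy summaries, including immunohistochemistry (IHC), on ITT.

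**The concern.** A disposition table should account for everyone who entered and explain who left. Here, entry to the table depends on having the primary measurement, so the subjects most in need of explanation are excluded by definition.

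The documents foresee such subjects. Consent may be withdrawn at any time (Protocol 6.4). Assessments and biopsy may need return visits over up to 3 days (Protocol 7.1, footnote 1). An examination before the procedure looks for intercurrent illness that raises risk (Protocol 3.1.1), and withdrawal because of an adverse event is anticipated (Protocol 7.3.7). With about 6 subjects, each one is worth 16.7 percentage points.

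The Safety set raises a related, smaller question. One ataluren dose selects nobody, because eligibility already requires it: "Currently being treated with ataluren 10, 10, 20 mg/kg", for at least 9 months. Yet the events being counted are dated from the biopsy.

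**Working it through.** The plan gives no sample-size calculation, power or error rate, so there is no figure to reproduce. The check is of set membership, with arithmetic on the planned 6 subjects (Protocol 5.1). The documents give no rate of withdrawal or assay failure; the rates below are assumptions.

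**1. Who is in the disposition table.** Take 6 enrolled, with the other 5 completing and having valid ECL results. The study ends for a subject with the follow-up call at about 1 week (Protocol 3.4).

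| Sixth subject | In ITT? | Table on ITT | Table on Enrolled |
|---|---|---|---|
| Withdraws, never a valid ECL result | No | 5/5 (100%) completed, no reason | 5/6 (83.3%) completed, 1/6 (16.7%) discontinued, with reason |
| Takes the call, never a valid ECL result | No | 5/5 (100%) completed | 6/6 (100%) completed |
| Withdraws after biopsy, sample later validly assayed | Yes | 5/6 completed, 1/6 discontinued | Same |

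The deciding condition is whether a valid ECL result ever exists. With m withdrawals of the first kind, ITT shows (6 − m)/(6 − m) = 100% for any m below 6. Enrolled shows (6 − m)/6: 83.3%, 66.7% and 50.0% for m = 1, 2, 3.

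**2. How often a subject could be missing.** If each subject independently lacks a valid ECL result with probability q, the chance of at least one among 6 is 1 − (1 − q)^6. For assumed q = 5%, 10%, 20% and 30% this gives 26.5%, 46.9%, 73.8% and 88.2%. This covers completers as well as withdrawals.

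**3. A dependency on the word enrolled.** SAP 4.2 turns on screen failure, which is not defined, and Protocol 4.2 lists as an inclusion criterion: "Willing to undergo muscle biopsy". A subject who qualifies and then declines could be placed on either side. If he is called a screen failure, Enrolled also reads 5/5, and he appears only as 1 of 6 in Screened.

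**4. TEAE denominator.** An unbiopsied subject has no biopsy date, so he cannot have a TEAE but does count in Safety. With 6 in Safety, 5 biopsied and one subject with a TEAE: 1/6 = 16.7% on Safety against 1/5 = 20.0% of those biopsied, a difference of 3.3 points. The exact 95% intervals, 0.4–64.1% and 0.5–71.6%, largely overlap. If all 5 biopsied subjects had a TEAE, the table would show 5/6 = 83.3%.

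**5. IHC.** A subject leaves the IHC tables only if all his ECL samples are invalid. SAP 7.1 plans several locations, multiple cores and multiple samples; reading each as at least 2 gives 2 × 2 × 2 = 8. At an assumed independent failure rate of 50% per sample, 0.5^8 = 0.4% per subject, and 1 − (1 − 0.0039)^6 = 2.3% for any of 6. Values below the quantification limit are kept at half that limit (SAP 7).

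**The case against.** The best defence is that SAP 6.1 already counts each population, so a reader sees Enrolled 6 against ITT 5. That stands, but the count gives neither the reason nor whether the subject completed. SAP 5.1 promises listings only for selected domains and names none for disposition.

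A second defence is that Protocol 8.1 plans no hypothesis test and SAP 5.1 prints counts beside percentages. That also stands. No error rate or power is affected, and protocol and SAP agree on the ITT definition.

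Three stronger readings are tempting but not supported:

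- A reader might infer that anyone who leaves before his ECL result is available is lost from the table. He is not: samples go to a contract laboratory for analysis (Protocol 3.1.2), and a valid result obtained after he has left keeps him in ITT.
- A reader might infer that a failed or stopped biopsy is a hidden discontinuation. Under Protocol 3.4 such a subject can still take the call and complete, so moving the table to Enrolled would not by itself reveal him.
- A reader might infer a material threat to the IHC endpoint. The figures above make loss very unlikely unless samples fail from a shared cause, and inadequate tissue could spoil IHC too.

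On safety, SAP 4.4 says all subjects rather than enrolled subjects, so a screen failure taking ataluren could be counted (1/7 = 14.3% against 1/6 = 16.7% with all 6 enrolled biopsied). Protocol 7.3.1 speaks of events in enrolled subjects, which makes that reading less likely.

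**Conclusion.** The point holds for disposition and demographics: as written, SAP 6.1 and 6.4 omit every enrolled subject who never has a valid ECL result, withdrawn or not. The size is one subject in 6: 100% completed instead of 83.3%, with the one discontinuation and its reason missing. This assumes that one enrolled subject withdraws without a valid result and is not classed as a screen failure.

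The TEAE mismatch is real but small, 3.3 points in the example. The IHC dependence would rarely have any effect.

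This concerns accuracy of reporting, and the priority is minor. Nothing changes if all enrolled subjects are biopsied with valid ECL results and no screen failure enters Safety.

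**What to change.** **Main change.** In SAP 6.1, base completion, discontinuation and reasons on the Enrolled population. Add a line for enrolled subjects with no biopsy or no valid ECL result and why, because such a subject may still complete the call. In SAP 4.2, define screen failure and say how a subject who declines the biopsy after qualifying is classed. In SAP 6.4, also show demographics on Enrolled, using Visit 1 values where there is no biopsy date. Protocol section 8 names no set for disposition or demographics, so this conflicts with nothing there.

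**Secondary.** In SAP 4.4, limit Safety to enrolled subjects. In SAP 8.1, use as the TEAE denominator those in whom the biopsy procedure was started. State also that Study 046 listings will not hold every adverse event, since events unrelated to the biopsy go to the parent-study case report form (Protocol 7.3.4 and 7.3.7, Table 4).

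**Optional.** Summarise IHC on enrolled subjects with at least one valid IHC result.

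Record changes to protocol-defined sets in SAP 10, which now reports no major changes.

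**Cost.** Mostly wording, using populations already defined. Whether the procedure was started must be recorded if it is not already. The n may differ between tables and needs a footnote.
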